1.2.4. Timing of outcome measures

The key timings for each comparison are:

- End of treatment: 42 days
- Primary outcome based on routine national data: 60 days
- Clinical outcomes based on data from care homes: 60 days
- End of follow-up based on routine national data: 120 days
- End of trial: Once last resident has reached 120 days and data cleaned and analysed.

The explanation for separating the assessment of the primary outcome from end of treatment is that outcomes following acute COVID infection can be delayed. The median (IQR) time from symptom onset to death based upon ONS data is 14 (0-28) days.[6] Hence, assessing the primary outcome at 60 days following randomisation maximises the likelihood that we'll capture most adverse events associated with the infection, this based on a median outbreak duration of 28 days.

There is evidence that some older people with COVID deteriorate as a consequence of deconditioning and loss of physical function following acute infection. These adverse effects are related to physical deconditioning, rather than the direct effect of the virus, but they could be ameliorated by preventative therapies that reduce the likelihood, duration or severity of COVID infection. We have therefore included a 120 day follow-up point using routinely collected NHS data to gather information on how study treatments modify longer-term adverse outcomes as a consequence of COVID-19, e.g. long-COVID.

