Electronic frailty index at 60 days	Electronic frailty index (eFI) The eFI is presented as a score (e.g. if 9 deficits are present out of a possible total of 36 the FI score = 0.25) - higher scores indicate increasing frailty. The eFI score is used to define frailty categories: - Fit (0 - 0.12) - Mild frailty (> 0.12 - 0.24) - Moderate frailty (> 0.24 - 0.36) - Severe frailty (> 0.36) A composite endpoint strategy will be used to handle the eFI outcome truncated due to death by adding an extra category for death to ensure that death equates to the worst outcome.	-	✓	Ordered categorical	Mixed-effect ordinal logistic regression
Ordinal outcome for the most serious event experienced during the 120 days post- randomisation	Four-level ordinal outcome: No SARS-CoV-2 infection, SARS-CoV-2 infection but resident remains in care home, Admission to hospital, all- cause and Death, all-cause.	✓	✓	Ordered categorical	Mixed-effect ordinal logistic regression
Clinical: care home level					

Page **14** of **25**

Written using WPD 16.5 version 3.0, 13-Sep-2018. Effective date: 13-Oct-2018. Template Author: [name]

Outcome measures	Description	Sourc	es	Type of data	Analysis method
Number of SARS-CoV-2 infections in residents in the care home	Aggregate infection rate in the care home. The numerator will be all confirmed SARS-CoV-2 infections including residents not participating in PROTECT-CH trial and the denominator will be the number of residents in the care home at randomisation.	✓	~	Rate (Proportion)	Linear regression (rate difference) and Poisson regression (rate ratio)
Additional Safety:					
Serious Adverse Reactions (SAR, excluding primary and secondary outcomes) and Suspected Unexpected SAR (SUSAR)		✓			
Adverse events relevant to the intervention as specified in relevant IMP specific appendix to protocol		✓			

*For PEP- only applicable for residents not positive at randomisation; [†]excludes residents with directive for no hospitalisation

Page **15** of **25**

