7.4. Secondary outcomes

Table 1 lists all the secondary outcomes and the type of variables.

Individual-level secondary outcomes will be analysed using mixed-effects regression models appropriate for the type of outcome variable, adjusting for minimisation variables and individual-level factors including age, sex, and vaccination status as fixed effects with a random effect for care home.

Ordered categorical outcomes will be analysed similarly as the primary outcome.

Continuous outcomes will be analysed using linear mixed-effect model, with further adjustment for baseline outcome measure if available. The estimated between group effect will be presented using the adjusted difference between means, along with a 95% confidence interval.

Binary variables will be analysed using mixed effects logistic regression model. The between group effect will be reported using an adjusted risk difference and adjusted risk ratio along with corresponding 95% confidence intervals, obtained using Stata's Margins command with standard errors computed using the delta method.

All-cause mortality (time to death) will be analysed using mixed-effects Cox regression model (shared frailty model). A Kaplan-Meier curve will be presented by trial arm. Other time-to-event outcomes will be analysed using competing-risks survival regression with cluster–robust standard errors. The between group effect will be reported using an adjusted hazard ratio along with a corresponding 95% confidence interval. Estimated cumulative incidence function graphs will be presented for each of the outcomes by trial arm.

The care home level infection rate outcome will be analysed using multiple linear regression of the cluster proportions, adjusted for the cluster-level minimisation variables, to obtain the adjusted difference in mean rates between the intervention and control arms along with the corresponding 95% CI. Poisson regression on cluster-level rates, adjusted for the cluster-level minimisation variables, will be used to obtain estimated rate ratio with corresponding 95% CI. The regression models will be weighted by the inverse of the variance of each cluster summary to take account of variability in cluster size. For this outcome, there will be no adjustment for individual-level covariates since not all residents will have individual level infection data to allow for individual-level analysis.

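### The 60-day electronic frailty index is analysed only in four bands plus death, which loses some precision, mainly if many residents are severely frail

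*SAP*

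**What the plan says.** SAP section 2.4, Table 1, describes the eFI as a proportion of deficits, with a worked example: "if 9 deficits are present out of a possible total of 36 the FI score = 0.25". It then states that "The eFI score is used to define frailty categories" and sets four bands: "Fit (0 - 0.12) - Mild frailty (> 0.12 - 0.24") and "Moderate frailty (> 0.24 - 0.36) - Severe frailty (> 0.36"). Residents who die before day 60 are handled by "adding an extra category for death to ensure that death equates to the worst outcome". The outcome is typed as ordered categorical and assigned a mixed-effect ordinal logistic regression.

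SAP section 7.4 says "Ordered categorical outcomes will be analysed similarly as the primary outcome". The covariates for the primary outcome (section 7.1) are the minimisation factors, age, sex and vaccination status. Adjustment for the outcome's own baseline value appears only in the sentence on continuous outcomes: "Continuous outcomes will be analysed using linear mixed-effect model, with further adjustment for baseline outcome measure if available". Baseline eFI is nonetheless among the resident-level characteristics listed in SAP section 5.2.

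Protocol section 2.2 lists the eFI at 60 days without mentioning bands. No analysis of the uncut score appears elsewhere: the sensitivity analyses (SAP 7.2) cover the primary outcome only, and the supplementary analyses (SAP 7.5) cover the primary outcome and time to infection.

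**The concern.** A score with 37 possible values is reduced to four levels before analysis, and the SAP gives no reason. The ordinal model does not need the reduction, because the score is already ordered. The rule for deaths does not need it either, because death can be ranked above 36/36 as easily as above the severe band.

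The top band is open-ended. A resident with 13 deficits and one with 25 are treated as the same, and a severely frail resident who worsens registers only by dying. (Improvement from 13 to 12 deficits does register.) If many residents are in that band, much of the spread in the outcome is set aside.

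At stake is the precision of one secondary comparison. A null result on the bands would be weaker evidence of no effect on frailty than it might look, most of all in a very frail population.

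**Working it through.** **1. Reproducing the SAP's figure.** 9/36 = 0.25, as stated.

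**2. Bands in deficits.** 0.12 × 36 = 4.32, 0.24 × 36 = 8.64 and 0.36 × 36 = 12.96. The bands are therefore fit 0-4, mild 5-8, moderate 9-12 and severe 13-36.

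**3. Steps that change band.** Of the 36 steps from k to k+1 deficits, only 4→5, 8→9 and 12→13 cross a cut. So 33 of 36 (92%) do not, and within severe (13 to 36) 0 of 23 do.

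**4. Information kept under the analysis as planned.** The count in step 3 is not the information lost, because the model compares 60-day levels between arms. A small shift in the distribution still carries some residents across a cut. The loss therefore has to be simulated.

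Inputs:
- 15% deaths, the SAP section 2.1 planning value, taken as equal in both arms.
- Assumed, because the documents give no figures: baseline deficits normal with SD 4; mean new deficits 1.0 on standard care and 0.7 on treatment; no clustering; no adjustment for baseline eFI.
- Rank comparison of the arms, standing in for the proportional-odds model.

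Information kept = (z banded / z full score)². The share already severe at baseline is the normal probability above 12.5; at mean 11, for example, 1 − Φ((12.5 − 11)/4) = 1 − Φ(0.375) = 35%.

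| Mean deficits | Severe at baseline | Information kept | Lost |
|---|---|---|---|
| 9 | 19% | about 86% | 14% |
| 11 | 35% | about 75% | 25% |
| 13 | 55% | about 56% | 44% |
| 15 | 73% | about 30% | 70% |

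Repeat runs agree to within about two percentage points. With 0.5 against 0.2 new deficits the shares kept are 87%, 79%, 61% and 37%. With 1,000 residents per arm at means 9, 11 and 13, power is about 21%, 22% and 21% on the full score and 19%, 17% and 13% on the bands.

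**5. A milder case.** If the treatment acted through one common odds ratio at every cut, including death, information is proportional to 1 − Σp̄³ (the Whitehead formula cited for the sample size). Take an assumed beta-binomial eFI with mean 0.30 and SD 0.10, and 15% deaths. The survivors' bands are 0.03, 0.24, 0.42 and 0.31. Multiplied by 0.85 and with death added, the levels are 0.026, 0.204, 0.357, 0.264 and 0.15. The sum of cubes is 0.076, so the information is 0.924. The bands keep 0.932 of the full-score value. Across mean eFI 0.15 to 0.35 they keep 88-94%, then 79% at 0.40 and 63% at 0.45.

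**6. If baseline eFI were adjusted for in both versions.** With proportional-odds fits on the inputs of step 4, the bands keep about 45%, 35% and 22% at means 9, 11 and 13. With 1,000 per arm, power is 37% against 80%, 33% against 73%, and 28% against 77% (bands against full score).

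**The case against.** The bands are set in advance, easy to interpret and unbiased, and ranking death worst is sound. SAP section 7 calls secondary outcomes supportive. All of that stands, and it limits the point to precision.

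Four stronger readings are tempting, and the documents do not support them.

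- *That 33 of 36 unregistered steps means most of the information is lost.* It does not. The comparison is of levels, and steps 4 and 5 show modest losses unless the population is very frail.
- *That the banding cuts power from 73-80% to 28-37%.* Those figures require adjustment for baseline eFI, which the SAP states only for continuous outcomes.
- *That a null result would be caused by the cut-offs.* On the planned, unadjusted basis the full score also has only about 20-22% power in this scenario. The larger obstacle is the spread between residents, which baseline adjustment would reduce.
- *That the eFI is the trial's measure of deconditioning.* Protocol section 1.2.4 does say that "some older people with COVID deteriorate as a consequence of deconditioning and loss of physical function following acute infection", but uses this to justify the 120-day follow-up on routine data. It does not name the eFI.

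A further fair objection is cost. The eFI inherits the proportional-odds check and the non-proportional extension from SAP section 7.1. Five levels give four cut-points; a lightly merged full score plus death could give twenty or more.

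**Conclusion.** The point holds as a minor one. The SAP analyses a finer ordered score only in coarse bands, gives no reason, and plans no analysis of the uncut score. Under the planned unadjusted model, the loss in the scenario of equal deaths and fewer new deficits is about 14% of the information at a mean of 9 deficits, 25% at 11, 44% at 13 and 70% at 15. It is smaller if one odds ratio also covers death. All of these sizes rest on assumed frailty distributions and effects, so the documents cannot settle which applies; the direction, a greater loss with more severe frailty, can be relied on.

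The banding and the missing baseline adjustment should be dealt with together. Adjusting the bands alone would leave most of the gain unrealised, and moving to the full score without adjustment would gain little in the less frail scenarios. The adjusted figures are probably optimistic, since they assume that baseline eFI is recorded without error.

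**What to change.** In SAP Table 1, define the 60-day eFI outcome as the full ordered score, with sparse extreme scores merged by a rule fixed in advance and death as the worst level. Keep the mixed-effects ordinal logistic regression. State in section 7.4 that this model also adjusts for baseline eFI. Report the four bands plus death by arm descriptively.

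The data, model family and handling of death stay the same. The costs are more cut-points to estimate, a more cumbersome check of proportional odds, and an odds ratio read on a finer scale. The SAP should therefore say how that check will be done for this outcome.

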2.1. Sample size and justification

A total of 530 residents per group are required to detect an odds ratio of 0.67 for a 4-level ordinal primary outcome (no infection proportion 60%, infection remain in CH 15%, all-cause hospitalisation 10%, all-cause mortality 15%), assuming a two-sided significance level of 5% and 90% statistical power, with no adjustment for clustering [2].

Care homes of varying size will be included, and the number of residents recruited per care home will likely be in the range 20–60. Assuming an intra-cluster correlation of 0.11, a coefficient of variation for care home size of 0.49 (Lothian population analysis in 189 care homes[3]) and an average of 32 residents per care home in the study (assuming that the average number of beds per care home is 40[4] and that not all residents will take part in the study), this gives rise to a design effect or inflation factor of 5.25[5].

Therefore, to compare a single active treatment versus usual care, we will need in the region of 174 care homes, i.e., in excess of 5,500 residents. Allowing for the uncertainty surrounding the parameters listed above (e.g. levels of mortality and transmission rates are expected to be different in the second wave due to improved preparedness, better treatments and the potential impact of the expected vaccination programme, therefore it is possible that the observed proportions in the control group may differ), we propose a sample size of 200 care homes and a total number of residents in the region of 6,400 per comparison, with sample size re-estimation during the trial (once 60-day outcome data are available for at least 75% of residents randomised to standard care).

Therefore, comparing three active (unrelated) treatments concurrently versus standard care (in a 1:1:1:1 allocation ratio) would require 400 care homes in total, corresponding to around 13,000 residents.

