Outcome measures	Description	Sourc	ces	Type of data	Analysis method
Participant receives dexamethasone in the care home for COVID-19	Use of dexamethasone in care home for COVID- 19	\checkmark	-	Time-to- event	Competing-risks survival regression with cluster– robust standard errors
Participant receives oxygen in the care home for COVID-19	Use of oxygen in care home for COVID-19 (for care homes with capacity to give oxygen)	\checkmark	-	Time-to- event	Competing-risks survival regression with cluster– robust standard errors
Time to SARS-CoV-2 infection* - positive PCR or lateral flow test (or equivalent) (i) with symptoms of COVID-19 (ii) without symptoms of COVID-19, (iii) Total, i.e., either with or without symptoms of COVID-19.	Time from randomisation to SARS-CoV-2 infection - positive PCR or lateral flow test (or equivalent). The date of the LFT test will be used as the date of event if LFT is positive and confirmed by the PCR test. (i) with symptoms of COVID-19 (ii) without symptoms of COVID-19 (iii) with/without symptoms of COVID-19	✓ (presence/ absence of symptoms)	✓ (PCR test results)	Time-to- event	Competing-risks survival regression with cluster– robust standard errors
Time to first admission to hospital [†]	Time from randomisation to first hospitalisation for any reason	\checkmark	~	Time-to- event	Competing-risks survival regression with cluster– robust standard errors
Cause specific hospital admission		\checkmark	~		Descriptive
Days alive and not in hospital †		-	✓	Continuous	Linear mixed-effect model
Time to death	Time from randomisation to death (all-cause) in days	\checkmark	✓	Time-to- event	Shared frailty model

PROTECT-CH (2033) Statistical Analysis Plan Final version 1.0 02-Aug-2021. Based on protocol version 1.0 Page 13 of 25

Written using WPD 16.5 version 3.0, 13-Sep-2018. Effective date: 13-Oct-2018. Template Author: [name]

Outcome measures	Description	Sourc	es	Type of data	Analysis method
Cause-specific mortality, including COVID-19, stroke, pulmonary embolism, myocardial infarction	COVID-19	~		Binary	Descriptive
	stroke			Binary	Descriptive
	pulmonary embolism		•	Binary	Descriptive
	myocardial infarction			Binary	Descriptive

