4.2. Analysis sets

Outcome	Analysis set
Primary, secondary and safety outcomes – individual-level	Contemporaneously randomised care homes and their eligible residents analysed according to the group their care home was randomly allocated to regardless of adherence to trial allocation (Intention-to-treat [ITT] analysis population).
	Since not all residents will be eligible for all trial interventions, residents in homes allocated to standard care will only be included in a given comparison if they were eligible to be given the intervention of interest had their home been randomised to it (i.e. not taking the intervention of interest, or another drug in the same class, and did not have any contraindications to it).
	In the case where an outbreak based on a positive result from a lateral flow test is not confirmed with a PCR test, then the site remains in the trial in the ITT analysis population.
	Primary analysis will be for participants with complete outcome data collected (i.e., without imputation for missing data).
Care home level infection rate	All residents in contemporaneously randomised care homes including residents not consenting to PROTECT-CH included in the comparison.

Outcome	Analysis set		
Supplementary analyses (for	All residents with consent regardless of whether		
primary outcome and the	eligible/took part in treatment phase of trial, analysed according to the group their care home was randomly allocated.		
secondary outcome related to			
transmission (time to SARS-			
CoV2 infection))			

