5.2. Baseline characteristics

Baseline characteristics for cluster and individual participant levels will be summarised both overall and by treatment groups using appropriate descriptive statistics for continuous (mean, standard deviation, median, lower & upper quartiles, minimum, maximum and number of observations) and categorical (frequency counts and percentages) characteristics to illustrate balance between the groups at baseline. Baseline summaries will be based on the principal comparisons (between each treatment group and the concurrent standard care group respectively).

Cluster-level characteristics will include:

- Minimisation variables
 - care home type (residential vs nursing vs nursing and residential dual registration)
 - prior COVID-19 in care home at any time (yes vs no)
 - size of care home Total number of residents in care home (small (<30 residents), medium (>30, <50 residents), large (>50 residents))
 - care home has capacity to give oxygen (yes vs no)
- Any residents in care home received vaccination against COVID-19
- Any staff in care home received vaccination against COVID-19
- Country
- Care home ownership
- Registered for clients with learning disabilities
- CQC rating (outstanding, good, requires improvement) or equivalent in devolved administrations.
- Time between positive test for COVID-19 in resident/member of staff and care home randomisation (For PEP only)

Individual resident level baseline demographic and clinical characteristics will include:

- Age
- Sex
- Ethnicity
- BMI (from height and weight)
- Advance directive for no hospitalisation
- Do Not Attempt Resuscitation order
- Smoking status
- Co-morbidities (diabetes, heart disease, chronic lung disease, severe liver disease, severe kidney impairment, dementia, stroke)
- Previous positive test for COVID-19
- Tested positive for COVID-19 at randomisation (For PEP only)
- Received vaccination for COVID-19
- Time in care home
- Electronic frailty index
- Type of consent

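### Residents with a no-hospitalisation directive are dropped from days alive and out of hospital, although their deaths count fully in it; the cost is a different target population, not bias

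*SAP*

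**What the plan says.** SAP Table 1 (section 2.4) puts the same dagger on two secondary outcomes. One is time to first admission, described as "Time from randomisation to first hospitalisation for any reason" and analysed by competing-risks regression. The other is "Days alive and not in hospital", a continuous outcome taken from routine data only and analysed with a linear mixed model. The footnote "excludes residents with directive for no hospitalisation". It gives no reason and no date by which the directive must exist.

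SAP 4.2 defines its intention-to-treat population as "Contemporaneously randomised care homes and their eligible residents analysed according to the group their care home was randomly allocated to". That population serves every outcome in the row labelled "Primary, secondary and safety outcomes – individual-level", and the section mentions no exception for a directive. SAP 5.2 lists "Advance directive for no hospitalisation" among the resident-level baseline characteristics.

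Protocol 2.2 lists the days-alive outcome without any exclusion. The SAP's changes-from-protocol table, as far as its text can be read, has no entry for it. The primary ordinal outcome and time to death carry no dagger. For the frailty index, Table 1 adds a category so that death is scored as the worst result.

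**The concern.** A footnote that fits one outcome has been extended to another that works differently. A resident with a directive has little chance of an admission, so leaving such residents out of time to first admission is sensible. Days alive and out of hospital has two components, and only the hospital one is limited for these residents. Their survival is observed in full and counts in full.

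At stake is what the result describes. With the exclusion, the estimate applies only to residents without a directive. It then sits beside a primary outcome and a mortality outcome that cover everyone, and it answers a narrower question than the one in the protocol. Deaths that the trial will have recorded also leave this analysis.

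**Working it through.** **1. The plan's own figures.** The SAP gives no figure for this outcome, so only its general inputs can be checked. SAP 2.1 states: "A total of 530 residents per group are required to detect an odds ratio of 0.67". The standard-care assumptions are "no infection proportion 60%, infection remain in CH 15%, all-cause hospitalisation 10%, all-cause mortality 15" per cent.
- Whitehead formula, n per group = 6(z_α + z_β)² / [ln(OR)² (1 − Σp̄³)], at two-sided 5% and 90% power: 542 for OR 0.67 and 529 for OR 2/3. Both are within 3% of 530.
- Design effect: 1 + [(0.49² + 1) × 32 − 1] × 0.11 = 5.255, against 5.25 stated.
- Homes: 1,060 × 5.25 / 32 = 173.9, against 174 stated.

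The planning inputs reproduce and are used below.

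**2. How directive holders are treated across outcomes.**

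| Outcome | Does a holder's death count? | Admission limited for holders? | Holders included? |
|---|---|---|---|
| Primary ordinal, 60 days | Yes, top level | Yes | Yes |
| Ordinal, 120 days | Yes, top level | Yes | Yes |
| Time to death | Yes, the event | Not relevant | Yes |
| Time to first admission | Only as a competing event | Yes | No |
| Days alive and out of hospital | Yes, all days after death | Yes | No |

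A holder who dies on day 20 loses 60 − 20 = 40 days, the same as a resident without a directive who dies that day at home. The last row is treated like the fourth, although it resembles the first two more closely.

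**3. Death's share of lost days.** Inputs from SAP 2.1: 15% die, and 10% have admission as their worst event. Assumptions, because the documents do not give them: mean day of death d and length of stay L.
- Days lost to death per resident: D = 0.15 × (60 − d).
- Days lost to hospital: H = 0.10 × L if only the worst-event admissions have a stay. H = 0.25 × L if everyone who died was also admitted first.
- Share = D / (D + H).

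With d = 30, D = 4.5:

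| L (days) | Stay in survivors only | Stay in decedents too |
|---|---|---|
| 5 | 4.5/5.0 = 90% | 4.5/5.75 = 78% |
| 10 | 4.5/5.5 = 82% | 4.5/7.0 = 64% |
| 15 | 4.5/6.0 = 75% | 4.5/8.25 = 55% |
| 20 | 4.5/6.5 = 69% | 4.5/9.5 = 47% |

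The two components are equal at L = 45 days (4.5/0.10) in the first case and 18 days (4.5/0.25) in the second. With later deaths (d = 40, D = 3.0), survivors-only stays of 20 days give 3.0/5.0 = 60%. Stays of 15 days in decedents too give 3.0/6.75 = 44%.

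**4. Deaths dropped.** Let f be directive prevalence and r the mortality of holders relative to others (both assumed). Share of deaths dropped = f·r / (1 − f + f·r).
- r = 1: the share equals f. At f = 10% that is 48 of the 0.15 × 3,200 = 480 deaths expected under standard care in one comparison. At f = 30% it is 144.
- r = 1.5: 0.15/1.05 = 14% at f = 10%, and 0.45/1.15 = 39% at f = 30%.

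**5. Precision.** Carry the ICC of 0.11 over to this outcome (assumed). With 100 homes per arm, effective size per arm is 100 × 32 / 5.255 = 609. With 30% excluded, mean cluster size is 22.4, the design effect is 1 + (1.2401 × 22.4 − 1) × 0.11 = 3.95, and effective size is 2,240 / 3.95, about 568. OR 0.67 takes deaths from 15.0% to 10.6% and worst-event admissions from 10.0% to 7.7%. At a 10-day mean stay, the difference is 1.56 days with an approximate SD of 12.2. Power is about 61% with everyone and 58% with 30% excluded, holding the difference and SD fixed.

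**The case against.** A reader might infer that the footnote breaks the SAP's own intention-to-treat definition. That is too strong. SAP 4.2 is the general rule, and Table 1 sets other outcome-specific limits beside it: for post-exposure trials, time to infection covers only residents not already positive at randomisation, and oxygen use covers only homes able to give it. A specific footnote can qualify a general rule. What is missing is a reason and a cross-reference.

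A reader might also infer bias between arms. If the directive is the one in the baseline list of SAP 5.2, the restriction is on a pre-randomisation characteristic and the randomised comparison is preserved. Concern would arise only if directives made after randomisation counted, since care home staff know the allocation (SAP 2.2). The footnote leaves the date open, but nothing in the documents says that later directives count.

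The best substantive defence is that, for holders, the outcome reduces almost to days alive, so limiting it to residents in whom both components can occur is a coherent target. That is a fair choice to make openly. It loses force because the SAP accepts the same limitation in both ordinal outcomes and keeps these residents there.

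It also stands that the dropped deaths still count in the primary outcome, time to death and the 120-day outcome, and that SAP section 7 treats secondary outcomes as supportive.

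**Conclusion.** The point holds as a mismatch between an exclusion and an outcome. It affects one secondary outcome and leaves the primary result untouched. The harm is a target population that differs from the primary outcome, time to death and the protocol's version of this outcome, with a modest loss of information.

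Death is probably the larger component: roughly 55–90% of lost days with a mean day of death of 30 and stays of 5 to 15 days, depending on whether those who died were first admitted. It would be wrong to call the outcome death-driven without qualification. The 10% counts worst events only, so hospital days of residents who later died are not in it, and with long stays or late deaths the share falls below half.

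It is also tempting to say that a large fraction of deaths is lost, such as the 14–39% above, or that holders are the frailest residents. The documents give neither the prevalence of directives nor mortality among holders, so neither statement is supported. What can be said is that the share dropped equals the prevalence if mortality is equal, and exceeds it if holders die more often. The power loss is about three percentage points in an approximate calculation, because clustering dominates.

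**What to change.** In SAP Table 1, remove the dagger from the days-alive outcome so that it is analysed in the full intention-to-treat set of section 4.2. Keep the directive-excluded set as a sensitivity analysis. Retain the dagger for time to first admission, and state that it refers to the directive recorded before randomisation. If the sponsor prefers the exclusion for both outcomes, the exception and its reason should be written into section 4.2 and the changes-from-protocol table.

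The cost is SAP wording and one further model run. Directive status is already a listed baseline item and the outcome comes from routine data, so nothing new is collected. The downside is that the hospital component is close to zero for directive holders, so the full-set estimate leans more on survival. The sensitivity analysis shows how much that matters.
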